15.2. APPENDIX 2: EFFICACY OUTCOME MEASURES

15.2.1. *Multiple Sclerosis Functional Composite (MSFC)*

The original MSFC is a three-part, standardized, quantitative, assessment instrument for use in clinical studies, particularly clinical trials, of MS (Cutter et al, 1999). The MSFC initially included three components: T25FW, 9HPT, and the Paced Auditory Serial Addition Task [PASAT] and was designed to reflect the varied clinical expression of MS across patients and over time on three areas: leg function/ambulation, arm/hand function, and cognitive function.

Modifications were made to the MSFC which now consists of a 4-component test battery that includes T25FW, 9HPT, LCLA, and SDMT. The PASAT was replaced with the SDMT and the LCLA was added to test visual acuity. The scores for each area should change relatively independently over time. Administration time will vary depending upon the ability of the participant.

Total administration time for all three measures should be approximately 20-30 minutes. The MSFC can produce scores for each of the three individual measures as well as a composite score.

15.2.2. *Timed 25 Foot Walk (T25FW)*

The T25FW is a quantitative mobility and leg function performance test based on a timed 25-walk. It is the first component of the MFSC to be administered at each visit. The participant is directed to one end of a clearly marked 25-foot course and is instructed to walk 25 feet as quickly as possible, but safely. The time is calculated from the initiation of the instruction to start and ends when the participant has reached the 25-foot mark. The task is immediately administered again by having the patient walk back the same distance. Participants may use assistive devices when doing this task.

Administration time will vary depending upon the ability of the patient. Total administration time should be approximately 1-5 minutes. The score for the T25FW is the average of the two completed trials. This score can be used individually or used as part of the MSFC composite score.

15.2.3. *9-Hole Peg Test (9-HPT)*

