6.7.3. Change from Baseline

Change from baseline is calculated as (post-baseline result – baseline result).

Percent change from baseline is calculated as (change from baseline/baseline result)*100 as long as baseline is non-zero. If baseline is 0, change from baseline is defined as missing.

If either the baseline or the post-baseline result is missing, the change from baseline and/or percentage change from baseline is set to missing as well.

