6.8. Handling of Missing Data

Missing values with the exception of dates will not be imputed.

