If a participant could not use one hand at the outset and could use it subsequently, a baseline value of the worst occurring 9HPT in the same either dominant or nondominant arm will be used to impute the baseline value.

A similar approach is used for second composite with all 4 elements of the MSFC.

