3. STUDY ASSESSMENTS

3.1 Handling of Safety or Efficacy data

- If subject discontinues during study (Early Termination) at any visit, then any collected (safety and efficacy) data under EOS/Visit 7 (Week28) will be re-mapped to nearest scheduled visit as per Schedule of Assessment (SoA). If this visit has data already recorded then data will be remapped to the next visit following this nearest visit. This is applicable for all safety and efficacy analysis.
- No imputations will be performed on missing efficacy or safety data except for visits as defined in the SAP. Sensitivity analyses may be performed with imputations after the database is locked.
- The baseline visit will be defined as the most recent assessment prior to receiving the first treatment at Visit 3 considering scheduled and unscheduled visits.
- Handling of unscheduled visits for Laboratory and Vital Summary by timepoints- In change from baseline (CFB), % CFB and Abnormality analysis by visit tables, data collected at unscheduled visits will not be summarized since there are only 2 subjects with unscheduled visit data at pre-treatment visits and no unscheduled post-treatment.

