5. EFFICACY ANALYSES

Efficacy data from T25FW and 9HPT is available from the CLIMB registry for matched progressive MS patients. In addition MRI data was also collected from matched patients in the CLIMB registry data. Analysis from the BCT-101 study will compare results with the CLIMB registry data. Since data for patients in the CLIMB registry was collected at only two timepoints 1 to 2 years apart, each patient's outcome data will be adjusted by assuming linear change between the two timepoints to estimate the change at 28 weeks (i.e. by determining the slope or change in outcome per week using the two timepoints and then using baseline value + 28 weeks

times this slope to determine the estimated value at 28 weeks). Since the change may not be linear other functions may also be explored.

5.19-Hole Peg Test (9-HPT)

Dominant and non-dominant hand will be analyzed separately in addition to together as mentioned in SAP section 9.2.

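### A patient who can no longer walk 25 feet drops out of the T25FW and MSFC mean changes, which moves them towards improvement; the combined 9-HPT also has no formula that covers a lost hand

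*SAP*

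**What the plan says.** - **T25FW score.** Protocol 15.2.2: "The score for the T25FW is the average of the two completed trials". SAP 9.2 also averages two trials. Neither gives a maximum time or a score for a patient who cannot finish. The 60-second limit in Protocol 3.1 applies only at entry.
- **Missing values.** SAP 6.7.3: "If either the baseline or the post-baseline result is missing, the change from baseline and/or percentage change from baseline is set to missing". SAP 6.8: "Missing values with the exception of dates will not be imputed". SAP Appendix I, 3.1: "No imputations will be performed on missing efficacy or safety data except for visits as defined in the SAP".
- **MSFC.** The formulas in SAP 9.6 and Appendix I, 5.3 each contain a walk term. SAP 9.6 defines the 9-HPT term as the average of a right-hand and a left-hand reciprocal.
- **9-HPT outside the MSFC.** Appendix I, 5.1: "Dominant and non-dominant hand will be analyzed separately in addition to together as mentioned in SAP section 9.2". SAP 9.2 describes the test but does not say how the two hands are combined.
- **Inability.** The only rule is in SAP 9.6, under the MSFC, and opens: "If a participant could not use one hand at the outset and could use it subsequently, a baseline value of the worst occurring 9HPT". It imputes a baseline from that arm, and concerns a hand regained, not one lost.
- **Other provisions.** SAP 9.2 scores only deaths related to progression or treatment as non-response. Sensitivity analyses in SAP 9.5.1 and Appendix I, 3.1 are optional and name no method.

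**The concern.** In progressive MS, a walk that cannot be completed is an outcome, and usually the worst change in the group. The stated rules treat it like a test that was not done. Removing that patient raises the mean of those who remain, in speed, in seconds and in the MSFC.

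The study is open-label, and SAP 5.1 says efficacy will be evaluated while it runs. A scoring rule chosen late would therefore be chosen with results in view. The 20 patients are meant to inform a randomized study (SAP 4.3), so a favourable tilt in the mean changes would carry into its planning.

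The undefined combined 9-HPT is a lesser worry. It feeds the responder endpoint, and one possible reading turns a lost hand into a gain.

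**Working it through.** There is no sample-size or power figure to reproduce, because SAP 4.3 makes no formal calculation. The check follows the rules and then sizes the effect.

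**1. What the rules do with a lost walk.** No completed trial means no T25FW score. The change is then missing (SAP 6.7.3) and is not imputed (SAP 6.8; Appendix I, 3.1). The walk term is absent, so neither MSFC composite can be computed at that visit.

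**2. Whether the event is foreseeable.** Entry allows EDSS up to 6.5 (Protocol 3.1). The next step, 7.0, is a walking limit of about 5 m even with aid (Protocol Table 3). The course is 25 × 0.3048 = 7.62 m. One half-point step from the entry ceiling can therefore make the test impossible.

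**3. Size in ft/s.** The documents give no loss rate, mean change or starting speed for such patients, so these are assumptions. Take 20 patients, k lost walks and the others at mean m. The plan reports m. Scoring each loss as 0 ft/s from starting speed s gives

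mean = [m(20 − k) − k·s] / 20.

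The slowest speed allowed at entry is 25/60 = 0.417 ft/s; 1.0 ft/s is taken as a higher start.

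| Others' mean (= planned result) | k | s = 0.417 | s = 1.0 |
|---|---|---|---|
| +0.10 | 1 | +0.074 | +0.045 |
| +0.10 | 2 | +0.048 | −0.010 |
| +0.05 | 2 | +0.003 | −0.055 |
| +0.20 | 2 | +0.138 | +0.080 |

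Example: (0.10 × 18 − 2 × 0.417)/20 = 0.048.

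**4. Size as percent change in speed.** A post-baseline 0 ft/s with a positive baseline is −100%, which SAP 6.7.3 can compute. With the others at 0%, two losses give (0 × 18 − 200)/20 = −10% instead of 0%. With the others at +5%, they give (90 − 200)/20 = −5.5% instead of +5%.

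**5. Combined 9-HPT, if averaged over the surviving hand only.** Let a be the faster and b the slower hand's baseline time, r = b/a, with the slower hand wholly lost and the faster one unchanged. The apparent gain in mean time is

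1 − 2a/(a + b) = (r − 1)/(r + 1).

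- 25 s and 40 s: 23.1%
- 30 s and 50 s: 25.0%
- 25 s and 50 s: 33.3%

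The gain reaches 25% when r ≥ 2/0.75 − 1 = 1.67. Losing the faster hand gives the same figure as a worsening. One false responder would be 1/20 = 5 percentage points.

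**6. The responder endpoint and a lost walk.** A patient without a walk time cannot be a T25FW responder. SAP 6.4 bases percentages on all subjects in the group, so a lost walk then counts as no improvement on that test. SAP 9.2 does not state this denominator for the endpoint itself.

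**The case against.** **Only complete inability is lost.** Neither test has a time cap in the documents, and assistive devices are allowed for the walk, so severe slowing is still scored. This stands, and it limits how often the problem can arise.

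**The effect is small.** With an assumed SD of 0.3 ft/s, the standard error is 0.3/√20 = 0.067. One loss shifts the mean by 0.026 to 0.055, and two by 0.052 to 0.110. The planned median moves less: in simulation with that SD it falls from +0.10 to about +0.06 with two losses. This also stands as to weight. But the shift is a bias in one direction, not noise.

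**The worsening would be visible elsewhere.** EDSS, the ambulation functional-system shift table, MSWS-12 and the subject listings would show it, and SAP 6.1 requires the number with missing data in the tables. That count does not separate patients unable to do the test from patients not tested. The eCRF may record the reason, but it is not among these documents.

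**The lost hand is not a false gain in the MSFC.** A reader might infer that the MSFC would average over the surviving hand. SAP 9.6 names two reciprocals, so with one absent SAP 6.7.3 and 6.8 point to a missing score. The baseline imputation for a regained hand would hardly be needed if one hand sufficed. This objection succeeds, and the surviving-hand concern is confined to the combined 9-HPT outside the MSFC. Even there the separate-hand analysis would expose the loss.

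**Conclusion.** The lost-walk point holds. Followed as written, the rules remove a patient who can no longer walk 25 feet from the T25FW and MSFC mean changes, and so favour improvement. The figures rest on an assumed number of losses, starting speed and mean in the others. Two losses in 20 with the others at +0.10 ft/s turn a reported +0.10 into +0.048 to −0.01.

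The 9-HPT point is secondary. A false responder needs an undefined average taken over one hand, complete loss of the slower hand, a baseline ratio of at least 1.67 and an essentially unchanged other hand.

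Two stronger readings are not supported. A reader might infer that lost walks inflate the primary efficacy endpoint; they do not if all mITT subjects are the denominator. A reader might also infer a favourable bias against the registry, since "Efficacy data from T25FW and 9HPT is available from the CLIMB registry" for comparison. Its direction is uncertain, because a registry patient without a second time has no slope and drops out too.

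The weight is minor to moderate: safety is primary, and mainly secondary endpoints are affected.

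**What to change.** Add an exception to SAP 6.8 and Appendix I, 3.1 for post-baseline tests not completed because of MS:

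1. Score T25FW speed as 0 ft/s (−100%) in the ft/s mean changes. Do not use 0 as a baseline score, since SAP 6.7.3 says "If baseline is 0, change from baseline is defined as missing".
2. Define the combined 9-HPT as requiring both hands, and never average over the surviving hand only.
3. Count the patient as not improved on that test at that visit, and keep all mITT subjects in the responder denominator.
4. Report the number unable by test and visit, separately from tests not done for other reasons.

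For T25FW and 9-HPT in seconds and for the MSFC, report observed data with the number unable, plus a prespecified sensitivity analysis that scores inability as a worst value. State whether the SAP 9.6 baseline imputation for a regained hand survives Appendix I, 3.1. Apply the same handling of inability on both sides of the registry comparison.

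The cost is one SAP paragraph, one reason code and slightly less favourable mean changes. A lost walk still leaves the main MSFC analysis and the means in seconds, so these must be read with the number unable and the sensitivity result.

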9.7. Summary of Reasons for Efficacy Non-Evaluability/Exclusion from Efficacy Analyses

The EE population will be defined based upon doses administered and compliance to protocol to determine whether a subset of the 20 subjects may be analyzed as the EE population, to better evaluate efficacy of NurOwn in progressive MS.

1. BACKGROUND

This document contains additional details that are prespecified as an Appendix to the BCT-101 US safety and efficacy analyses in the statistical analysis plan finalized on April 12, 2019.

The word Treatment will be used instead of Transplant or Transplantation across all study TFLs since it more closely reflects the mechanism of action of the investigative product. The SAP uses the terms NurOwn® or MSC-NTF. For all Tables and Figures the term NurOwn® will be used to distinguish the investigational product from other types of Mesenchymal Stem Cells. The database have the value of NurOwn which is what is displayed in the listings, if needed.

2. ANALYSIS POPULATIONS

Per SAP section 6.5.3, key efficacy analysis on efficacy evaluable (EE) population will not be performed as the difference between EE and modified intent-to-treat (mITT) population is minimal. Additional sub-populations may be analyzed to explore efficacy in subgroups after the database is locked.

3. STUDY ASSESSMENTS

3.1 Handling of Safety or Efficacy data

- If subject discontinues during study (Early Termination) at any visit, then any collected (safety and efficacy) data under EOS/Visit 7 (Week28) will be re-mapped to nearest scheduled visit as per Schedule of Assessment (SoA). If this visit has data already recorded then data will be remapped to the next visit following this nearest visit. This is applicable for all safety and efficacy analysis.
- No imputations will be performed on missing efficacy or safety data except for visits as defined in the SAP. Sensitivity analyses may be performed with imputations after the database is locked.
- The baseline visit will be defined as the most recent assessment prior to receiving the first treatment at Visit 3 considering scheduled and unscheduled visits.
- Handling of unscheduled visits for Laboratory and Vital Summary by timepoints- In change from baseline (CFB), % CFB and Abnormality analysis by visit tables, data collected at unscheduled visits will not be summarized since there are only 2 subjects with unscheduled visit data at pre-treatment visits and no unscheduled post-treatment.

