4.5. PHYSICAL EXAMINATIONS, VITAL SIGNS, AND ELECTROCARDIOGRAMS

Participants will undergo a physical examination at the Screening (Visit 1), at each transplantation visit (Visit 3, Visit 4 and Visit 5), and at the last study visit (V7). Height will be measured at Screening (Visit 1), whereas body weight will be measured at Screening (Visit 1) and Visit 7. Vital Signs measurements (including blood pressure, body temperature, pulse and respiration rate after sitting for at least 3 minutes) will be monitored at Screening (Visit 1) and at all in-clinic visits through Visit 7.

Standard 12-Lead electrocardiogram ECG will be performed at Visit 1. ECG results must be manually read, preferably by a cardiologist, and the results entered on the electronic case report form (eCRF).

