9.3.5. Safety analyses

All safety analyses will be based upon the Safety Population.

All AEs will be coded to System Organ Class (SOC) and Preferred Term (PT) using the Medical Dictionary for Regulatory Activities (MedDRA®). The number of treatment-emergent adverse events (TEAEs) and the number of participants with any TEAEs (along with percentages) will be tabulated by SOC and PT.

A TEAE is an AE that occurs for the first time after initiation of treatment or if it had occurred prior to treatment, worsens in severity after initiation of treatment.

Separate summaries will be provided for the following categories of AEs:

- TEAEs
- TEAEs by severity
- Treatment-related TEAEs
- Serious TEAEs

When evaluating changes in safety parameters, Baseline will be defined as the last measurement prior to first transplantation (i.e., prior to initiation of treatment).

Abnormalities in hematology, blood chemistry and ECG assessments will be summarized.

MRI (T1 and T2 weighted images) will be assessed for study safety at baseline and at the end of the study.

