1 MS Medical History to collect type and duration of MS symptoms and Date of Diagnosis

2 Pulse rate, Blood pressure (Respiratory rate, Body temperature)

3 Hematology: Complete blood count (red blood cells with indices, white blood cells with differential and platelet count, hemoglobin, hematocrit)

4 Blood Biochemistry: At V1 and V7: Sodium, potassium, chloride, glucose, BUN, creatinine, bicarbonate, calcium, total bilirubin, AST, ALT, alkaline phosphatase, uric acid, total cholesterol, HDL, LDL. At V3, V4 and V5: sodium, potassium, chloride, glucose, BUN, creatinine

5 Coagulation: PT, PTT, INR.

6 Urinalysis - Specific Gravity, pH, glucose, protein, ketones, blood.

7 EDSS-Expanded Disability Status Scale.

8 MSFC including T25FW and 9-HPT

9 Symbol Digit Modality Test (SDMT).

10 12 item MS Walking Scale (MSWS-12).

11 An Early Termination (ET) visit will be conducted only for participants who discontinue the study after the first treatment, post Visit 3. The ET visit will include all the procedures required at study Visit 7.

BrainStorm Cell Therapeutics Ltd.
Statistical Analysis Plan - Protocol BCT-101-US

April 12, 2019

Table 3: Detailed Schedule of Assessments for Cell Transplantation Visits (V3, V4, and V5)

Estimated Time	xx:00-yy:00	12:00	14:00	20:00	08:00	12:00
Time\ Procedure	Up to 8 hours before transplant	Hr. 0	Hr. 2 (\pm 15 minutes)	Hr. 8 (\pm 15 minutes)	Hr. 20 (\pm 30 minutes)	Discharge/up to Hr. 24
Admit to In-patient Facility	✓					
Physical Examination	✓					✓
Concomitant medication review	✓					✓
Hematology ³	✓					
Blood biochemistry ⁴	✓					
Coagulation ⁵	✓					
Blood collection for biomarkers	✓				✓	
Vital signs ²	✓		✓	✓	✓	✓
Adverse events review ⁶	✓		✓	✓	✓	✓
Cell Transplant IT		✓				
Retention of CSF sample		✓				
Visual inspection of injection site			✓		✓	
Discharge from Inpatient Setting						✓

Abbreviations: BUN = blood urea nitrogen, CSF = cerebrospinal fluid, INR = international normalized ration, IT = intrathecal, PT = prothrombin time, PTT = partial thromboplastin time

*Hematology, biochemistry and coagulation labs are to be drawn and checked before transplant

**To be determined for each study site

1. Hematology: Complete blood count (red blood cells with indices, white blood cells with differential and Platelet count, hemoglobin, hematocrit)
3. Sodium, potassium, chloride, glucose, BUN, creatinine
4. Coagulation - PT, PTT, INR
5. Pulse rate, Blood pressure (Respiratory rate, Body temperature)

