8.7. MRI analysis

MRI Data will be analyzed for safety by looking at the following change from baseline to end of study:

- Mean Changes in number of new or enlarging FLAIR lesions on MRI
- Percentage of subjects with $\geq 1, \geq 2, \geq 3$ new or enlarging FLAIR lesions on MRI
- Mean Changes in active FLAIR lesions (new + enlarging) on MRI
- Percentage of subjects with $\geq 1, \geq 2, \geq 3$ active FLAIR lesions (new + enlarging) on MRI
- Mean Change in Total volume of new FLAIR lesions on MRI
- Mean Change in Total volume of FLAIR lesions on MRI

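### The early-termination re-mapping in SAP Appendix I 3.1 does not exempt items scheduled only at Visits 1 and 7, so a leaver's exit MRI, weight and wider chemistry can move off the end-of-study timepoint

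*SAP*

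**What the plan says.** SAP Appendix I, section 3.1, deals with participants who discontinue. For them, "any collected (safety and efficacy) data under EOS/Visit 7 (Week28) will be re-mapped to nearest scheduled visit as per Schedule of Assessment (SoA". If the destination is taken, the rule continues: "If this visit has data already recorded then data will be remapped to the next visit following this nearest visit". Its scope is total: "This is applicable for all safety and efficacy analysis". No assessment is exempted.

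The exit visit is a full one. Footnote 11 to SAP Table 2 states: "The ET visit will include all the procedures required at study Visit 7".

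Several of those procedures exist only at the two ends of the schedule:
- In both Schedules of Assessments, MRI, urinalysis, weight, neurological examination and C-SSRS are ticked at V1 and V7 only. For weight, Protocol 4.5 confirms that "body weight will be measured at Screening (Visit 1) and Visit 7".
- The full chemistry panel, including AST, ALT, alkaline phosphatase and bilirubin, is taken at V1 and V7. The treatment visits have six analytes ("At V3, V4 and V5: sodium, potassium, chloride, glucose, BUN, creatinine"), and V6 has no chemistry at all.

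On analysis, SAP 8.7 says that "MRI Data will be analyzed for safety by looking at the following change from baseline to end of study". Protocol 9.3.5 agrees: "MRI (T1 and T2 weighted images) will be assessed for study safety at baseline and at the end of the study". SAP 8.3 and 8.4 summarise laboratory values and vital signs, including weight, at each post-baseline timepoint. The shift tables in SAP 8.3 instead take the worst post-baseline value and are expressly not by visit.

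**The concern.** The re-mapping rule suits assessments repeated at every clinic visit, such as T25FW or EDSS. It does not suit items measured once before treatment and once at the end. For those, the exit value is the only post-treatment measurement, and the rule gives it the label of a visit at which the item is not scheduled.

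MRI is the most exposed. It is part of the primary safety endpoint (SAP 3.2.1), its safety analysis has one post-baseline timepoint, and there is no by-visit table to pick up a scan relabelled V4, V5 or V6. If the programmer selects end-of-study scans by visit label after re-mapping, the MRI summary loses early leavers although their scans were taken.

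For weight, the wider chemistry, and urine pH and specific gravity, the Week 28 row loses the leaver's value. A row based on one or a few people appears at Week 8, 16 or 22.

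**Working it through.** The plan gives no figure to reproduce: there is no sample size calculation, dropout rate or count of leavers. The check applies the rule to each possible exit time.

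**Inputs.** Clinic visits are at Weeks 0 (V3), 8 (V4), 16 (V5), 22 (V6) and 28 (V7), from the Schedule of Assessments. Planned N is 20.

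**Assumptions.** Visits fall on their nominal weeks, the leaver attended every clinic visit due before exit, telephone visits are set aside, and exit time is uniform over the 28 weeks. The last is a device for measuring the window, not a forecast.

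The text leaves two things open: whether a destination counts as already filled by visit or by item, and whether a scheduled visit means any visit or one where the item is due. That gives three readings.

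**Reading 1: nearest visit, occupancy judged by visit.** A past visit is always filled, so the data move forward to the next one.

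| Exit in weeks | Destination | Share of window |
|---|---|---|
| 0–8 | V4 | 8/28 = 28.6% |
| 8–16 | V5 | 8/28 = 28.6% |
| 16–22 | V6 | 6/28 = 21.4% |
| 22–28 | V7 | 6/28 = 21.4% |

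Moved off V7: 22/28 = 79%.

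**Reading 2: nearest visit, occupancy judged by item.** A V1/V7-only item is never already recorded at V3 to V6, so the nearest visit always takes it. The boundaries are the midpoints 4, 12, 19 and 25.

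| Exit in weeks | Destination | Share of window |
|---|---|---|
| 0–4 | V3 | 4/28 = 14.3% |
| 4–12 | V4 | 8/28 = 28.6% |
| 12–19 | V5 | 7/28 = 25.0% |
| 19–25 | V6 | 6/28 = 21.4% |
| 25–28 | V7 | 3/28 = 10.7% |

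Moved off V7: 25/28 = 89%. Exits in the first four weeks land on V3, the day of first treatment.

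**Reading 3: nearest visit at which the item is scheduled.** The candidates are V1 and V7. V1 is filled, so the value goes to V7. Moved off V7: 0%.

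**Effect on the denominator.** With 20 treated and k leavers moved, the end-of-study n is 20 − k. Each leaver costs 1/20 = 5%. For k = 1 to 4, an assumed range, n runs from 19 to 16.

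**What happens to each item once moved.**

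| Item | Planned output | Effect of the move |
|---|---|---|
| MRI | Baseline to end of study only (SAP 8.7) | May have no place in the summary |
| Weight | By timepoint (SAP 8.4) | Moves to another row |
| AST, ALT, ALP, bilirubin, other V1/V7-only chemistry | By timepoint, plus shift tables (SAP 8.3) | Moves row; stays in the shift tables |
| Urine pH, specific gravity | As other laboratory values (SAP 8.3) | Moves row |
| Other urinalysis, C-SSRS, neurological examination | Listings only (SAP 8.3, 8.8, 8.9) | Label changes only |

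**The case against.** The strongest reply is that little is lost. The shift tables keep an abnormal exit liver value whatever its label. Out-of-range values have their own listing, with clinically significant ones flagged. All data are listed, and the AE tables do not depend on visit labels. Weight and chemistry are relocated, and a Week 10 value is closer in time to Week 8 than to Week 28. All of this stands. A reader might infer that leavers' exit safety data vanish from the safety summaries; the documents do not support that.

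For MRI, SAP 8.7 names the end of study, not Visit 7, and Protocol 8.2 calls a leaver's return visit the End of Study visit (Visit 7), so the exit scan could simply be used. Appendix I 5.4 also analyses MRI for efficacy without naming a visit. This makes the loss uncertain but does not remove the conflict. Both schedules head V7 as the end-of-study visit, SAP 4.1 places the MRI there, and Appendix I 3.1 takes that label away.

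It can also be said that the schedule is an item-by-visit grid, so the rule was meant item by item (Reading 3). That is possible. But the occupancy sentence speaks of a visit holding data, which fits Reading 1 better, and nothing states the item-level intention.

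The number affected may be small. Appendix I section 2 calls the difference between the EE and mITT populations minimal, and EE requires all three treatments, so few mITT members can have left before the third dose. This does not bound exits between Weeks 16 and 22, after all three doses.

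**Conclusion.** The point holds as a conflict between a stated rule and the planned end-of-study analyses. On the plain visit-level reading, every exit before Week 22 moves the V1/V7-only items to V4, V5 or V6; exits after Week 22 stay at V7. The exit MRI may then be left out of the SAP 8.7 summary. Tabulated weight, wider chemistry, and urine pH and specific gravity leave the Week 28 row.

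The size is 5% of the end-of-study denominator per leaver moved, and the number of leavers is not given. The shares of 79%, 89% and 0% rest on nominal visit weeks and a uniform exit time. They mainly show how far the outcome depends on an unstated reading. No lesion rate is given, so the effect on the MRI percentages cannot be calculated.

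Three further inferences are tempting and go beyond the documents:
- That the MRI summary will certainly include completers only. It depends on how end of study is programmed.
- That telephone visits will receive exit data. A completed call already holds adverse-event and medication data, so under the visit-level rule the values pass on to the next visit; a telephone visit could be the destination only if the call was missed or occupancy is judged by item.
- That leavers are mainly people with safety problems. Protocol 8.2 also lists insufficient cell numbers, participant request, and investigator or sponsor discretion.

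The correction is worth making because MRI belongs to the primary safety endpoint and the remedy is small.

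**What to change.** Add two statements to SAP Appendix I 3.1:

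1. An early-termination value is re-mapped only to a visit at which the Schedule of Assessments lists that assessment.
2. For tabulated items measured only at V1 and V7 (MRI, weight, the wider chemistry panel, urine pH and specific gravity), the early-termination value is kept as the end-of-study value in SAP 8.3, 8.4 and 8.7, and the interval from first treatment is shown in the listing.

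Under these statements no early-termination value of a V1/V7-only item leaves the end-of-study timepoint. The items that are only listed need no change.

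The cost is two sentences and a small programming change, with no new data. The downside is that end-of-study intervals will vary for early leavers, so the 28-week summaries will contain some shorter exposures. This also matters for any MRI comparison with the registry patients in Appendix I section 5, whose outcomes are to be adjusted to 28 weeks. The listed interval lets a reader see which values are affected.
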